11.2 Subject demographics and other baseline characteristics

All data for background and demographic variables will be listed by treatment group and subject. Summary statistics will be provided by treatment group.

Relevant medical history, current medical conditions, results of laboratory screens, drug tests and any other relevant information will be listed by treatment group and subject.

All data for background and demographic variables will be listed by treatment and subject. Summary statistics will be provided for all subjects, as well as for each treatment sequence.

Relevant medical history, current medical conditions, results of laboratory screens, drug tests and any other relevant information will be listed by treatment sequence and subject.

11.3 **Treatments**

Data for study drug administration (rescue medication) and concomitant therapies will be listed by treatment group and subject.

11.4 **Analysis of the primary variable(s)**

Company Confidential Information

11.4.1 Variable(s)

Company Confidential Information

11.4.2 Statistical model, hypothesis, and method of analysis

Company Confidential Information

11.4.3 Handling of missing values/censoring/discontinuations

The repeated measures regression model can accommodate subjects with missing follow-up FEV1 and will produce valid estimates of mean and covariance parameters if the data are missing at random.

11.5 Analysis of secondary variable(s)

11.5.1 Efficacy / Pharmacodynamics

Company Confidential Information

11.5.2 Safety

Vital signs

All vital signs data will be listed by treatment group, subject, and visit/time and if ranges are available abnormalities (and relevant orthostatic changes) will be flagged. Summary statistics will be provided by treatment and visit/time.

ECG evaluations

All ECG data will be listed by treatment group, subject and visit/time, abnormalities will be flagged. Summary statistics will be provided by treatment and visit/time.

Clinical laboratory evaluations

All laboratory data will be listed by treatment group, subject, and visit/time and if normal ranges are available abnormalities will be flagged. Summary statistics will be provided by treatment and visit/time.

Adverse events

All information obtained on adverse events will be displayed by treatment group and subject.

The number and percentage of subjects with adverse events will be tabulated by body system and preferred term with a breakdown by treatment. A subject with multiple adverse events within a body system is only counted once towards the total of this body system.

Other safety evaluations

Pregnancy test results will be listed by treatment group, subject and visit/time.

11.5.3 Pharmacokinetics

11.5.4 Other assessments

Company Confidential Information

11.6 Analysis of exploratory variables

11.7 Sample size calculation

Company Confidential Information

11.8 Interim analyses

12 Ethical considerations

12.1 Regulatory and ethical compliance

This clinical study was designed and shall be implemented, executed and reported in accordance with the ICH Harmonized Tripartite Guidelines for Good Clinical Practice, with applicable local regulations (including European Directive 2001/20/EC, US Code of Federal Regulations Title 21, and Japanese Ministry of Health, Labor, and Welfare), and with the ethical principles laid down in the Declaration of Helsinki.

12.2 Responsibilities of the investigator and IRB/IEC

Before initiating a trial, the investigator/institution must obtain approval/favorable opinion from the Institutional Review Board/Independent Ethics Committee (IRB/IEC) for the trial protocol, written informed consent form, consent form updates, subject recruitment procedures (e.g. advertisements) and any other written information to be provided to subjects. Prior to study start, the investigator is required to sign a protocol signature page confirming his/her agreement to conduct the study in accordance with these documents and all of the instructions and procedures found in this protocol and to give access to all relevant data and records to Novartis monitors, auditors, Novartis Quality Assurance representatives, designated agents of Novartis, IRBs/IECs, and regulatory authorities as required. If an inspection of the clinical site is requested by a regulatory authority, the investigator must inform Novartis immediately that this request has been made.

For multi-center trials, a Coordinating Investigator will be selected by Novartis around the time of Last Patient Last Visit to be a reviewer and signatory for the clinical study report.

12.3 Publication of study protocol and results

The key design elements of this protocol will be posted in a publicly accessible database such as clinicaltrials.gov. In addition, upon study completion and finalization of the study report the results of this trial will be either submitted for publication and/or posted in a publicly accessible database of clinical trial results.

13 Protocol adherence

This protocol defines the study objectives, the study procedures and the data to be collected on study participants. Additional assessments required to ensure safety of subjects should be administered as deemed necessary on a case by case basis. Under no circumstances is an investigator allowed to collect additional data or conduct any additional procedures for any research related purpose involving any investigational drugs under the protocol.

Investigators ascertain they will apply due diligence to avoid protocol deviations. If an investigator feels a protocol deviation would improve the conduct of the study this must be considered a protocol amendment, and unless such an amendment is agreed upon by Novartis and approved by the IRB/IEC and health authorities, where required, it cannot be implemented.

Potential Hy's law cases	•	ALT or AST > 3 × ULN and TBL > 2 × ULN without initial increase in ALP to > 2 × ULN
ALT or AST elevation with coagulopathy	•	ALT or AST > 3 × ULN and INR > 1.5 (in the absence of anticoagulation)
ALT or AST elevation accompanied by symptoms	•	ALT or AST > 3 × ULN accompanied by (general) malaise, fatigue, abdominal pain, nausea, or vomiting, or rash, or eosinophilia
	•	ALT or AST > 8 × ULN
Isolated ALT or AST elevation	•	5 x ULN < ALT/AST ≤ 8 x ULN
	•	3 x ULN < ALT/AST ≤ 5 x ULN
Isolated ALP elevation	•	ALP > 2 × ULN (in the absence of known bone pathology)
Others	•	Any clinical event of jaundice (or equivalent term)
Others	•	Any adverse event potentially indicative of liver toxicity

Table 15-2 Actions required for Liver Events

Criteria	Actions required
Potential Hy's Law case	
ALT or AST elevation with coagulopathy ALT or AST elevation accompanied by symptoms	 Discontinue the study treatment immediately Hospitalize, if clinically appropriate Establish causality
Isolated ALT or AST elevation > 8 × ULN Jaundice	Complete CRFs per liver event guidance
	 If confirmed, consider interruption or discontinuation of study drug
Isolated ALT or AST elevation > 5 to ≤ 8 × ULN	 If elevation persists for more than 2 weeks, discontinue the study drug
	Establish causality
	Complete CRFs per liver event guidance
Isolated ALT or AST elevation > 3 to ≤ 5 × ULN (patient is asymptomatic)	Monitor liver chemistry tests two or three times weekly
	 Repeat liver chemistry tests within 48-72 hours
Isolated ALP elevation	 If elevation is confirmed, measure fractionated ALP; if >50% is of liver origin, establish hepatic causality
	 Complete CRFs per liver event guidance
Any AE potentially indicative of liver	 Consider study treatment interruption or discontinuation
toxicity	Hospitalize if clinically appropriate
	Complete CRFs per liver event guidance

Table 15-3 Exclusion of underlying liver disease

Disease	Assessment	
Hepatitis A, B, C, E	 IgM anti-HAV; HBSAg, IgM anti-HBc, HBV DNA; anti-HCV, HCV RNA, IgM & IgG anti-HEV, HEV RNA 	
CMV, HSV, EBV infection	 IgM & IgG anti-CMV, IgM & IgG anti-HSV; IgM & IgG anti-EBV 	
Autoimmune hepatitis	 ANA & ASMA titers, total IgM, IgG, IgE, IgA 	
Alcoholic hepatitis	 Ethanol history, gGT, MCV, CD-transferrin 	
Nonalcoholic steatohepatitis	Ultrasound or MRI	
Hypoxic/ischemic hepatopathy	 Medical history: acute or chronic CHF, hypotension, hypoxia, hepatic venous occlusion. Ultrasound or MRI. 	
Biliary tract disease	 Ultrasound or MRI, ERCP as appropriate. 	
Wilson disease	Caeruloplasmin	
Hemochromatosis	Ferritin, transferrin	
Alpha-1-antitrypsin deficiency	Alpha-1-antitrypsin	

16 Appendix 2: Specific Renal Alert Criteria and Actions

 Table 16-1
 Specific Renal Alert Criteria and Actions

Criteria	Action required
Serum creatinine (sCr) increase 25 – 49% compared to baseline	 Consider causes and possible interventions Follow up within 2-5 days
Serum creatinine increase > 50%	 Consider causes and possible interventions Repeat assessment within 24-48h if possible Consider drug interruption or discontinuation unless other causes are diagnosed and corrected Consider hospitalization and specialized treatment
Protein-creatinine or albumin-creatinine ratio increase ≥ 2-fold or new onset dipstick proteinuria ≥ 1+ or Albumin-creatinine ratio (ACR) ≥ 30 mg/g or ≥ 3 mg/mmol; or Protein-creatinine ratio (PCR)≥ 150 mg/g or >15 mg/mmol	 Consider causes and possible interventions Assess serum albumin & serum protein Repeat assessment to confirm Consider drug interruption or discontinuation unless other causes are diagnosed and corrected
New onset glucosuria on urine dipstick (unless related to concomitant treatment, diabetes)	Assess & document: Blood glucose (fasting) Serum creatinine Urine albumin-creatinine ratio Assess & document:
New hematuria on dipstick	 Urine sediment microscopy Assess sCr and urine albumin-creatinine ratio Exclude infection, trauma, bleeding from the distal urinary tract/bladder, menstruation Consider bleeding disorder

Additional specialized assessments are available to assess renal function or renal pathology. (Note: In exceptional cases when a nephrologist considers a renal biopsy, it is strongly recommended to make specimen slides available for evaluation by Novartis to potentially identify project-wide patterns of nephrotoxicity.)

Whenever a renal event is identified, a detailed subject history and examination are indicated to identify, document and potentially eliminate risk factors that may have initiated or contributed to the event:

- Blood pressure assessment (after 5 min rest, with an appropriate cuff size)
- Signs and symptoms such as fever, headache, shortness of breath, back or abdominal pain, dysuria, hematuria, dependent or periorbital edema
- Changes in blood pressure, body weight, fluid intake, voiding pattern, or urine output
- Concomitant events or procedures such as trauma, surgical procedures, cardiac or hepatic failure, contrast media or other known nephrotoxin administration, or other potential causes of renal dysfunction, e.g., dehydration, hemorrhage, tumor lysis

Table 16-2 Follow-up of renal events

Action	Follow up	
Assess*, document and record in the Case Report Form (CRF) or via electronic data load. Review and record possible contributing factors to the renal event (co-medications, other co-morbid conditions) and additional diagnostic procedures (MRI etc) in the CRF.	 Urine dipstick and sediment microscopy Blood pressure and body weight Serum creatinine, electrolytes (sodium, potassium, phosphate, calcium), bicarbonate and uric acid Urine output 	
	 Event resolution: (sCr within 10% of baseline or protein-creatinine ratio within 50% of baseline) 	
Monitor subject regularly (frequency at investigator's discretion) until:	 or Event stabilization: sCr level with ±10% variability over last 6 months or protein-creatinine ratio stabilization at a new level with ±50% variability over last 6 months. 	

^{*} Urine osmolality: in the absence of diuretics or chronic kidney disease this can be a very sensitive metric for integrated kidney function that requires excellent tubular function. A high urinary osmolality in the setting of an increase in sCr will point toward a "pre-renal" cause rather than tubular toxicity.

## 1 Introduction

## 1.1 Scope of document

The RAP documents contain detailed information to aid the production of Statistics & Programming input into the Clinical Study Report (CSR) for trial "CJM112X2204".

The Statistical analysis plan (SAP) describes the implementation of the statistical analysis planned in the protocol.

Tables, Figures, Listings (TFL) details the presentation of the data, including shells of summary tables, figures and listings, and Programming Datasets Specification (PDS) contains programming specifications e.g. for derived variables and derived datasets, to support the creation of CSR and IA outputs.

## 1.2 Study reference documentation

Final study protocol (version v01) is available at the time of finalization of the original Statistical Analysis Plan and the version v02 of the study protocol is available at the finalization of SAP Amendment 3.

## 1.3 Study objectives

1.3.1 Primary objective

Primary objective	Endpoints related to primary objectives
• To determine whether treatment with CJM112 in patients with inadequately controlled moderate to severe asthma leads to an improvement in airflow obstruction.	

1.3.2 Secondary objective(s)

Secondary objective(s)	Endpoints related to secondary objectives
• To determine whether treatment with CJM112 in patients with inadequately controlled moderate to severe asthma leads to an improvement in FEV1% of predicted.	Change from baseline FEV % of predicted.
• To determine whether treatment with CJM112 in patients with inadequately controlled moderate to severe asthma leads to an improvement in asthma control.	• Change from baseline in ACQ score, % of patients with ≥ 0.5 decrease in ACQ score.
To assess the safety and tolerability of CJM112 in patients with inadequately controlled moderate to severe asthma.	Study treatment discontinuations and adverse events.

## 1.3.3 Exploratory objective(s)

## 1.4 Study design and treatment

This is a non-confirmatory, randomized, subject- and investigator-blinded, placebo-controlled, multi-center, parallel-arm study evaluating the efficacy of CJM112 on top of standard of care in patients with inadequately controlled moderate to severe asthma.

This study will enroll approximately 110 male and female patients between 18 and 75 years old with uncontrolled symptoms of moderate or severe asthma (defined by ACQ score of  $\geq$ 1.5) who are compliant on standard of care medications.

After an initial screening visit and run-in period of 4 weeks, subjects eligible per inclusion and exclusion criteria at the baseline visit will be randomized (3:2) to receive Company Confidential Information.

CJM112 or matching placebo subcutaneously over 3 months during visits at the clinical study site. All baseline safety evaluation results must be available prior to the first dose. After the end of the treatment period, subjects will be followed for an additional Site visits to administer dose and assess safety and efficacy will be scheduled as depicted in the figure below.

At least two interim analyses (IA) will be conducted, as further described below.

#### Figure 1-1 Study design

Company Confidential Information

# 2 First interpretable results (FIR)

# 3 Interim analyses

## 4 Statistical methods: Analysis sets

For subjects for which the actual treatment received does not match the randomized treatment the treatment actually received will be used for the analysis.

The safety analysis set will include all subjects that received any study drug.

The PK analysis set will include all subjects with at least one available valid (i.e. not flagged for exclusion) PK concentration measurement, who received any study drug and experienced no protocol deviations with relevant impact on PK data.

The PD analysis set will include all subjects with any available PD data and experienced no protocol deviations with relevant impact on PD or efficacy data. If a subject has an asthma exacerbation adverse event during the study, all subsequent efficacy assessments will be excluded from the PD analysis set.

The analysis sets and protocol deviation codes are related as follows:

Table 4-1 Protocol deviation codes and analysis sets

Category Deviation code	Text description of deviation	Data exclusion	
Subjects are exclude	ded from PD analysis in case of these PDs:	Exclude subject from PD analysis set	
INCL05	Deviation from inclusion criterion 5	Yes	
INCL07	Deviation from inclusion criterion 7	Yes	
EXCL01	Deviation from exclusion criterion 1	Yes	

Page 16

CJM112X2204

Category Deviation code	Text description of deviation	Data exclusion
EXCL02	Deviation from exclusion criterion 2	Yes
EXCL03	Deviation from exclusion criterion 3	Yes
EXCL07	Deviation from exclusion criterion 7	Yes
EXCL20	Deviation from exclusion criterion 20	Yes
EXCL21	Deviation from exclusion criterion 21	Yes
EXCL22	Deviation from exclusion criterion 22	Yes
COMD01	Use of prohibited medication during the study	Yes ( from this visit onwards)
WITHO1	Patient who met withdrawal criteria but were not withdrawn	Yes (from the visit subjects met withdrawal criteria onwards)

If updates to this table are needed, an amendment to the SAP will be implemented prior to DBL.

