7.2 Discontinuation of study treatment

Discontinuation of study treatment for a subject occurs when study treatment is stopped earlier than the protocol planned duration. Discontinuation of study treatment can be decided by either the subject or the investigator.

Study treatment must be discontinued under the following circumstances:

- Subject decision subjects may choose to discontinue study treatment for any reason at any time.
- The investigator believes that continuation would negatively impact the safety of the subject or the risk/benefit ratio of trial participation.
- Any protocol deviation that results in a significant risk to the subject's safety.
- Pregnancy (see Section 8.6 (Safety) and Section 9.6 (Pregnancy reporting))
- Adverse events, abnormal laboratory values or abnormal test result that indicate a safety risk to the subject.
- Patients who experience an asthma exacerbation during the treatment epoch that requires treatment with systemic corticosteroids.
- Patients with > 50% decrease in FEV₁ confirmed by a repeat measurement during the study period.
- Emergence of the following severe adverse events:
 - Severe, grade 3 or higher allergic or hypersensitivity reaction
 - Severe, acute, grade 3 or higher infection as judged by the investigator
 - Severe neutropenia grade 3 or higher
- If a liver or renal event occurs, follow guidelines outlined in Appendix 1 and Appendix 2 regarding discontinuation of study treatment.
- Any laboratory abnormalities that in the judgment of the investigator, taking into consideration the subject's overall status, prevents the subject from continuing participation in the study.

Treatment for patients experiencing an asthma exacerbation with systemic steroids is considered standard of care. The dose and duration for such treatment will be left at the discretion of the clinical site study investigator, so that appropriate treatment can be tailored to the severity of the patient's clinical condition. Treatment discontinuations due to asthma exacerbations will be considered "treatment failures".

Use of prohibited treatment as per Table 5-1 might result in treatment discontinuation (decision will be taken on case by case basis after consultation with Sponsor).

The appropriate personnel from the site and Novartis will assess whether investigational drug treatment should be discontinued for any subject whose treatment code has been broken inadvertently for any reason.

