If discontinuation of study treatment occurs, investigator must determine the primary reason for the subject's premature discontinuation of study treatment and record this information on the Dosage Administration CRF.

Subjects who discontinue study treatment or who decide they do not wish to participate in the study further should NOT be considered withdrawn from the study UNLESS they withdraw their consent (see Section 7.3, Withdraw of Informed Consent). Where possible, they should return for visits 201, 202 and 299. If they fail to return for these visits for unknown reasons, every efforts (e.g. telephone, e-mail, letter) should be made to contact the subject/predesignated contact as specified in Section 7.4 (Lost to follow-up).

The investigator must also contact the IRT to register the patient's discontinuation from study treatment.

After study treatment discontinuation, at a minimum, in abbreviated visits, the following data should be collected at clinic visits or via telephone/email contact:

- new / concomitant treatments
- adverse events/Serious Adverse Events

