#### Company Confidential Information

The inclusion of the data of subjects who miss at least one dose will be determined on a case-by-case basis, and will be decided during the Protocol Deviation assignment in a blinded fashion.

For spirometry assessments, a pre- and post-bronchodilator assessment should be conducted during baseline and at visits 105, 107, 201, and 299. Both short and long acting bronchodilators must be withheld prior to the study visits as described in the SOM, patients must be instructed to withhold bronchodilators (both short and long acting) prior to performing spirometry at applicable visits, as follows:

- Short-acting  $\beta$ 2-agonists (SABAs)  $\geq$  6 h
- SAMA  $\geq 8 \text{ h}$
- Long-acting bronchodilators (LABAs and LAMAs) given twice daily  $\geq 24 \text{ h}$
- Long-acting bronchodilators (LABAs and LAMAs) given once daily  $\geq 48 \text{ h}$

When bronchodilators are given combined with ICS, the ICS component will have to be withheld as well. When such situation arises, and rescheduling of the visit is not possible, the spirometry test results and other parameters that involves Spirometry results, e.g. ACQ7, will be omitted from analysis for that visit.

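### WITHO1 in SAP Table 4-1 removes the triggering visit itself, so a confirmed FEV1 fall of more than 50% can be deleted from the FEV1 data; the criteria it refers to are undefined

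*SAP*

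**What the plan says.** SAP section 4, Table 4-1, lists the deviations that remove data from the PD analysis set. WITHO1 is described as "Patient who met withdrawal criteria but were not withdrawn", and its data-exclusion entry is "Yes (from the visit subjects met withdrawal criteria onwards". The paragraph above the table has a separate rule for asthma exacerbation adverse events, which drops only the efficacy assessments that come after the event.

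The visible protocol has no list under the name *withdrawal criteria*. The nearest is Protocol 7.2, introduced by "Study treatment must be discontinued under the following circumstances". One item there is a greater than 50% "decrease in FEV₁ confirmed by a repeat measurement during the study period". The same section says that subjects who stop treatment "should NOT be considered withdrawn from the study UNLESS they withdraw their consent", and adds: "Where possible, they should return for visits 201, 202 and 299". Spirometry continues into follow-up. Under SAP 6.2, "a pre- and post-bronchodilator assessment should be conducted during baseline and at visits 105, 107, 201, and 299".

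Protocol 2.1 gives the primary endpoint as change from baseline in FEV1 in mL. SAP 6.2 relies on missing at random and says that other assumptions may be explored.

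**The concern.** If WITHO1 points to the Protocol 7.2 list, one of its triggers is an extreme value of the primary variable, and the exclusion starts at the visit where that value was recorded. The deviation is the failure to act on the reading, so the reading comes first and is not contaminated by it. Deleting it selects on the outcome.

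This matters for the repeated-measures analysis. Under missing at random, the chance that a value is missing may depend on observed data but not on the missing value itself. Here the deleted value is the reason for its own deletion, and the model would fill the gap from the patient's earlier, better visits.

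The undefined term is a second problem. The protocol separates stopping treatment from withdrawal, so a programmer could apply WITHO1 to two quite different groups of patients.

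**Working it through.** **Tracing the rule.** Take a patient with a confirmed FEV1 fall of more than 50% and apply Table 4-1 under the two possible meanings of *withdrawn*.

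| Situation | *Withdrawn* = treatment stopped under Protocol 7.2 | *Withdrawn* = left the study |
|---|---|---|
| Treatment stopped as required, patient stays in follow-up | WITHO1 does not apply; no other code is triggered by the fall | WITHO1 applies: triggering value and later values removed |
| Treatment continued | WITHO1 applies: triggering value and later values removed | WITHO1 applies: same removal |
| Either, with an earlier exacerbation adverse event | Value already removed by the exacerbation rule | Value already removed by the exacerbation rule |

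The first reading treats equal FEV1 falls differently according to what was done afterwards. The second also removes follow-up data, such as visits 201 and 299, from patients who were handled correctly. On both, WITHO1 can delete the triggering value.

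**Consistency of the start points.** An exacerbation that needs systemic corticosteroids is also a Protocol 7.2 criterion. A patient not stopped after one therefore falls under two SAP rules with different windows: the exacerbation rule keeps assessments up to the event, while WITHO1 drops the visit at which the criterion was met. COMD01 (prohibited medication) also starts at the visit concerned, but there the medication may affect that visit's reading. Under WITHO1 the reading precedes the deviation.

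**Scale.** The plan gives no figure that depends on this rule, so there is nothing to reproduce. The following is an illustration only.

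1. Allocation: about 110 patients at 3:2 gives 110 × 3/5 = 66 on CJM112 and 110 × 2/5 = 44 on placebo.
2. SD of FEV1 change, from SE × √n for each row of SAP Table 10-1: 0.259, 0.348, 0.455, 0.280, 0.337 and 0.314 L. Pooled with weights n − 1 (total 386): √(51.83/386) = 0.366 L.
3. SE of the difference: 0.366 × √(1/66 + 1/44) = 0.071 L, about 71 mL.
4. Baseline FEV1 is not given; 1.5 to 2.5 L is assumed, so an exactly 50% fall is 0.75 to 1.25 L.
5. Contribution of one such value to an arm mean, 0.5 × baseline / n: 0.75/66 = 11 mL to 1.25/66 = 19 mL on CJM112, and 0.75/44 = 17 mL to 1.25/44 = 28 mL on placebo.
6. Dropping rather than keeping the patient, when the others average m = 0.049 L (inverse-variance mean of Table 10-1): shift = (m + 0.5 × baseline)/n. This gives 0.799/66 = 12 mL to 1.299/66 = 20 mL on CJM112, and 0.799/44 = 18 mL to 1.299/44 = 30 mL on placebo.
7. Across both calculations the shift is about 11 to 30 mL, or 11.4/71.3 = 0.16 to 29.5/71.3 = 0.41 standard errors per patient.

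**The case against.** The strongest reply is that the rule will rarely bite. It needs a confirmed fall of more than 50%, a patient not stopped despite a mandatory rule, and no earlier exacerbation adverse event. Patients enter at roughly 40 to 90% of predicted, so such a fall takes them below 20 to 45%, and many would plausibly have an exacerbation recorded. The count among 110 may be zero. This stands and limits the expected size.

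Other limits also stand:

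- The protocol requires the fall to be "confirmed by a repeat measurement during the study period". If the repeat is at a later visit, the criterion is arguably met only then, and the first low value survives.
- That the primary FEV1 analysis uses the PD set is strongly implied, but the text that would say so is blacked out, as is the primary model. Simple arm means do not reproduce a repeated-measures model or any use of the historical prior.
- SAP 6.2 leaves data from subjects who miss a dose to a blinded case-by-case decision. If that covers early stopping, retention after correct stopping is not guaranteed either.
- The study is non-confirmatory, and the PD set excludes relevant deviations by design.

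Two stronger readings are tempting. A reader might infer that the low value is lost only if the site failed to stop treatment. The documents do not support that: the literal sense of withdrawal also catches patients correctly stopped, and an earlier exacerbation adverse event removes the value in either case. A reader might also infer a direction of bias from the higher infection rate on CJM112 in Protocol 3.7. Those were primarily non-serious upper respiratory infections, mostly mild or moderate, whereas the Protocol 7.2 criterion is grade 3 or higher.

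None of this explains why a reading made before the deviation should be deleted because of it.

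**Conclusion.** The concern holds in a limited form. As written, WITHO1 includes the triggering visit. If its criteria are those of Protocol 7.2, it deletes a confirmed FEV1 fall of more than 50% from the FEV1 data of a patient who was not stopped. That deletion depends on the outcome, conflicts with the missing-at-random assumption in SAP 6.2, and does not match the start point of the exacerbation rule. The link to Protocol 7.2 is an inference; the undefined term is a defect on either reading.

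The effect is about 0.2 to 0.4 standard errors per affected patient, given the assumed baseline range, simple arm means and the SD from Table 10-1. The number of such patients is unknown and probably small, and the direction of bias is uncertain. The point merits correction because it is cheap to settle before database lock, not because a large bias has been shown.

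**What to change.** SAP section 4 already provides for amending Table 4-1 before database lock. In that amendment:

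1. Start the WITHO1 exclusion after the visit at which the criterion was met, so that the triggering value always counts. For the FEV1 criterion, the later exclusion then follows an observed value, which sits better with missing at random. State whether the criterion counts as met at the first low reading or at the repeat.
2. Define *withdrawal criteria* by reference to the Protocol 7.2 treatment-discontinuation list, and reconcile this with the protocol statement that stopping treatment is not withdrawal. Patients correctly stopped and still in follow-up should not be caught.
3. Report the number of WITHO1 cases by arm.
4. Add a sensitivity analysis that keeps all values excluded under WITHO1.

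Removing the WITHO1 exclusion altogether is more debatable, because the main analysis would then keep all later on-treatment data from patients who should have been stopped; the sensitivity analysis covers that case.

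The cost is one table row, one definition, a count by arm and one extra run. The downside is that the main analysis keeps one more visit per affected patient. No clinical rule changes.
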